- 1) To compare adherence among persons across the three study arms.
- 2) To evaluate the safety, tolerability and acceptability of treatment in the three arms.

3. Background

Globally, an estimated 70 – 80 million persons are chronically infected with hepatitis C (HCV). Chronic hepatitis C is associated with long-term complications including liver cirrhosis, hepatocellular carcinoma and end-stage liver disease. Chronic hepatitis C is treatable and treatment can cure infection such that HCV RNA is undetectable and persons cannot transmit virus and risk for chronic complications decreases substantially. Treatment access has been hampered in much of the world in part due to the low efficacy and toxicity of the previous generation of regimens. The landscape of HCV treatment has changed dramatically over the past few years with the FDA approval of highly efficacious, non-toxic second generation direct acting antiviral agents. With these advances in treatment, questions have arisen about delivery of these agents among populations in resource-limited settings (RLS) given some of the inherent differences in HCV infected patients in these settings. Ideally, a treatment regimen for RLS should be pan-genotypic; thereby, not requiring HCV genotype testing which can be cost prohibitive and rarely available in these settings. Moreover, treatment delivery strategies need to optimize adherence particularly in populations that have had suboptimal adherence such as people who inject drugs (PWID).

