- Obtain blood samples for laboratory tests listed in Table 3
- Brief survey on quality of life and alcohol and drug use
- Chart review of YRG-JHU ICC data to document HIV and antiretroviral therapy status and engagement in opioid substitution therapy (OST)

4a5.6. Additional details on laboratory tests and clinical assessments at visits.

Table 3. Schedule of assessments:

	Screening	Baseline/ Day 1	End of treatment****	SVR 12*****
HCV RNA	X			X
HIV*	X			
HBsAg*	X			
IL 28b		X		
Prothrombin time	X	X		
α fetoprotein	X			
TSH**	X			
CBC with diff**	X			X
LFT**	X			X
RFT**	X			X
Complete physical exam	X			
Targeted Physical Exam		X	X	
Sample Storage	X		X	X
Adherence assessment***			X	

*HIV and HBsAg will only be done if the subject has not been tested in the past 3 months

**TSH = Thyroid stimulating hormone; CBC = complete blood count; LFT = Liver function tests; RFT = Renal function tests

****at 5 weeks for Arm 1, 12 weeks for Arms 2 and 3

*****At 17 weeks for Arm 1, 24 weeks for Arms 2 and 3

HCV RNA will be assessed using the Abbott Realtime HCV assay and will quantify the number of copies of HCV RNA per milliliter (copies/ml). Complete blood count (CBC) will include hemoglobin, total white blood cell (WBC) count, total lymphocyte count, packed cell volume, total red blood cell (RBC) count, differential count, erythrocyte sedimentation rate, mean corpuscular volume, mean corpuscular hemoglobin, mean corpuscular hemoglobin concentration and platelet count. Liver function tests (LFT) will include ALT, AST, total and direct bilirubin, total protein, serum albumin, serum globulin, albumin-globulin ratio, γ-GT and alkaline phosphatase.

Renal function tests

(RFT) will include blood urea nitrogen and serum creatinine. Plasma will be processed and stored at -70° C for future testing.

Complete physical examination: A complete physical examination will include documentation of general appearance and examination of the following body systems: head, neck and thyroid; eyes, ears, nose, throat, mouth and tongue; chest (excluding breasts); respiratory; cardiovascular; lymph nodes, abdomen; skin, hair, nails; musculoskeletal; neurological.

Targeted physical examination: This exam will focus on signs and symptoms related to liver disease.

Retinal examination: A fundoscopic retinal examination will be performed for those in Arm 1. This will be performed by the study doctor and the subject may be referred to a specialist if needed.

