Vital signs: Assessment of vital signs will include measurement of resting blood pressure, pulse, respiratory rate and temperature.

Pregnancy testing: All females of childbearing potential will have a urine pregnancy test at the Screening and Baseline visits.

Survey: We will use the EuroQOL-5D as well as the WPAI: Hepatitis C Quality of Life Surveys. These will be translated into the local language. While these surveys are intended to be self-administered, low literacy rates in our population will require that they be interviewer administered. We will also include brief questions on frequency of drug and alcohol use.

Chart Review: The YRG-JHU ICC maintains an electronic database to monitor client visits, test results and service utilization. Data that are available through this database will be abstracted from these patient records rather than collected de novo. Specifically, we are interested in HIV status and whether participants are engaged in antiretroviral therapy and/or opioid substitution therapy.

b. Study duration and number of study visits required of research participants.

Participants in all Arms will have 4 study visits (Screening, Baseline, End of Treatment and SVR12). Participants in Arm 1 will have an additional 3 visits for interferon injections, and participants in Arm 3 will have an additional two visits to pick up medication refills. The duration of the study will be 16 weeks for Arm 1 and 24 weeks for Arms 2 and 3.

c. Blinding, including justification for blinding or not blinding the trial, if applicable.

This study will not be blinded. In part, this is so that clinicians can appropriately monitor for side effects associated with pegylated interferon alfa-2a. The regimens delivered require different forms of delivery (e.g., pegylated interferon is an injectable medicine) and for different durations of time making blinding not feasible.

d. Justification of why participants will not receive routine care or will have current therapy stopped.

All participants will be able to receive the same routine medical care that they receive at the center and no other therapies will be stopped.

e. Justification for inclusion of a placebo or non-treatment group.

This study does not involve a placebo group.

f. Definition of treatment failure or participant removal criteria.

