Peglyated-interferon alfa-2a is commercially available as Taspiance by Emcure Pharmaceuticals in India and will be provided in this study as 180 µg/0.5 mL pre-filled syringes. Each syringe is to deliver 0.5 mL of drug product. The formulation, which is subcutaneously administered, contains sodium chloride, polysorbate 80, benzyl alcohol, sodium acetate trihydrate, acetic acid, and water for injection. The solution is colorless to light yellow and the pH is 6.0 ± 0.5.

Packaging and Labeling

The PEG will meet all applicable requirements of Good Manufacturing Practices: Manufacture of

investigational medicinal products (July 2003) and the Drug Controller General India (DCGI).

Storage and Handling

Peglyated-interferon alfa-2a prefilled syringes will be stored in the refrigerator at 2 °C to 8 °C (36 °F to 46 °F) protected from light and will not be frozen or shaken. Syringes are for single use only.

b. Justification and safety information if FDA approved drugs will be administered for non-FDA approved indications or if doses or routes of administration or participant populations are changed.

N/A

c. Justification and safety information if non-FDA approved drugs without an IND will be administered.

N/A

7. Study Statistics

a. Primary outcome variable.

The primary outcome will be sustained virologic response (SVR12), which is defined as HCV RNA < lower limit of quantification 12 weeks after treatment completion.

b. Secondary outcome variables.

Adherence for comparison across the three arms will be defined using a combination of the biometric data for Arms 1 and 2 and self-report and pill counts for Arm 3. Serious adverse events requiring dose modification or treatment discontinuation will include primarily laboratory abnormalities including anemia, neutropenia and thrombocytopenia. For any adverse event outcome, we will consider occurrence of any of the side effects commonly associated with treatment with pegylated interferon alfa-2a, including but not limited to fatigue, headache, pyrexia, myalgia, rigors, insomnia, nausea, alopecia, irritability, arthralgia, anorexia, dermatitis, depression, or fatigue.

c. Statistical plan including sample size justification and interim data analysis.

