All analyses will be conducted as intention to treat. We will use a chi-squared test of proportions to compare the proportions that achieve SVR12. Pairwise comparisons with correction for multiple comparisons will be conducted to directly compare Arms 1 and 2, Arms 1 and 3 and Arms 2 and 3. For secondary outcomes, chi squared tests of proportions will be used to compare categorical outcomes and a Wilcoxon rank-sum test will be used to compare adherence.

The primary objective of this study is to test the feasibility of DOT for HCV treatment among HCV-infected persons with substance use history in a resource limited setting. An additional objective is to generate pilot data to plan a larger powered study. We hypothesize that SVR12 will be higher in Arm 1 compared to Arms 2 and 3. Assuming a two-sided $\alpha=0.05$, 50 people in each arm and 70% achieving SVR12 in Arm 3, we will have >80% power to detect a difference of 25% (e.g., 95% completion in the SOF+DAC+PEG).

No interim analyses will be conducted as with 150 participants, it will not be possible to observe statistical differences prior to the completion of the trial.

d. Early stopping rules.

As we do not plan to do interim analyses, the only reason for stopping the trial would be a higher frequency than expected of serious adverse events. We will continually monitor the frequency of serious adverse events and if this frequency is 10% or higher, we will prematurely stop the trial.

8. Risks

a. Medical risks, listing all procedures, their major and minor risks and expected frequency.

It is anticipated that most participants who complete their full course of treatment with optimal adherence will clear hepatitis C from their bodies. However, for those individuals who do not respond to treatment, it is possible that non-response will affect their ability to respond to other drugs for hepatitis C in the future. However, with the newer direct acting antiviral (DAA) regimens, response rates have been demonstrated to be comparable in treatment naïve and prior non-responders. The primary risk related to taking these medications is with respect to side effects associated with pegylated interferon alfa2a.

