An AE is any untoward medical occurrence in a clinical investigation subject administered medicinal product and which does not necessarily have a causal relationship with this treatment. An AE can therefore be any unfavorable and unintended sign, symptom or disease temporally associated with the use of a medicinal product, whether or not considered related to the medicinal product.

AEs also include the following:

- Pre- or post-treatment complications that occur as a result of protocol mandated procedure (e.g., venipuncture) during or after screening (before the administration of study investigational medicinal product)
- Any pre-existing condition that increases in severity, or changes in nature during or as a consequence of the study investigational medicinal product phase of a human clinical trial will also be considered an AE.
- Complications and termination of pregnancy
- All AEs that occur from the study screening visit onwards and throughout the duration of the study, including the follow-up off study medication period will be recorded as an AE.

An AE does not include the following

- Medical or surgical procedures (e.g., surgery, endoscopy, tooth extraction, transfusion) performed; the condition that leads to the procedure is an adverse event.
- Pre-existing disease or conditions or laboratory abnormalities present or detected before the screening visit that do not worsen.
- Situations where an untoward medical occurrence has not occurred (e.g., hospitalization for elective surgery, social and/or convenience admissions)
- Overdose without clinical sequelae

- Any medical condition or clinically significant laboratory abnormality with an onset date before the consent form is signed and not related to a protocol-associated procedure is not an AE. It is considered to be pre-existing and should be documented on the medical history form.
- Uncomplicated pregnancy
- An induced elective abortion to terminate a pregnancy without a medical reason

8c1.1. Assessment of Adverse Events

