All SAEs will be recorded on the Serious Adverse Event report form and submitted within 24 hours of the principal investigator’s knowledge to both the US and the YRGCARE IRBs. For fatal or life-threatening SAEs, we will also include hospital case reports, autopsy reports or other hospital documents when applicable.

The principal investigator will take all therapeutic measures necessary for resolution of the SAE. Any medications necessary for treatment of the SAE will be recorded on the SAE form.

Follow-up of AEs will continue through the last day on study (including follow-up off-study medication period of the study) and/or until a conclusive outcome (e.g., resolved, resolved with sequelae, lost-to-follow-up, fatal) is achieved.

Participants who develop an SAE will be referred to the appropriate department within the Chattisgarh Institute for Medical Sciences (CIMS) as the ICC is on the campus of CIMS. This is a multi-specialty hospital, which has experts in medical gastroenterology, cardiology, nephrology, psychiatry, and urology among other specialties. Services available at CIMS are accessible by all YRGCARE patients and so we will use CIMS to manage all adverse events that cannot be managed directly at YRGCARE.

If a participant is injured as a result of being in this study, they will be given immediate treatment for injuries as per the standard of care at CIMS. The entire cost of health care and compensation due to study related injury or death will be taken care of by YRGCARE as per the order of the Licensing Authority in India (Drug Controller General India). This includes free medical management for as long as required and compensation to the family in the event of death. This is in compliance with the order specified in “Rule 122 DAB of the Drugs and Cosmetics Rules, 1945” and as per the Order from the Central Drugs Standard Control Organization.

d. Legal risks such as the risks that would be associated with breach of confidentiality.

Legal and social risks are possible in that study participants are PWID who engage in illegal activities. However, we will take multiple precautions to protect against breaches of confidentiality. No identifying information will be included in the electronic data capture methods. Interviewers will be trained to not discuss the participants of the study. Results will be reported in aggregate form only.

e. Financial risks to the participants.

N/A

9. Benefits

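### Any-AE proportions are compared by chi-squared tests without allowing for shorter follow-up in Arm 1 (16 or 17 weeks v 24), which can mask an interferon-related excess of common clinical AEs

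*Combined protocol and SAP*

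**What the plan says.** The second secondary objective (section 2) is "To evaluate the safety, tolerability and acceptability of treatment in the three arms".

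- **Outcome (7b).** It is binary: "For any adverse event outcome, we will consider occurrence of any of the side effects commonly associated with treatment with pegylated interferon alfa-2a". The list that follows consists largely of non-specific symptoms.
- **Test (7c).** For secondary outcomes, "chi squared tests of proportions will be used to compare categorical outcomes". No person-time rate, time-to-event method, common window or other exposure adjustment appears anywhere.
- **Recording period (8c1).** Events arising from screening onwards and "throughout the duration of the study, including the follow-up off study medication period will be recorded as an AE". Section 8c2.1 likewise carries AE follow-up to the last day on study.
- **Length of follow-up.** Section 4b: "The duration of the study will be 16 weeks for Arm 1 and 24 weeks for Arms 2 and 3". Section 4a5.5 agrees. The footnote to Table 3 places the SVR12 visit differently: "At 17 weeks for Arm 1, 24 weeks for Arms 2 and 3".
- **Visit content.** AE assessment is listed for the End of Treatment visit (4a5.3) and the early termination visit (4a5.4), but not for the 12-week post-treatment visit (4a5.5 and Table 3).
- **Surveillance (4a2, 8b).** Arm 1 has weekly clinic visits while on treatment. Arms 1 and 2 have daily field contact. Arm 3 attends at Weeks 4 and 8 for refills and then at end of treatment.

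**The concern.** A participant in Arm 2 or 3 has 24/16 = 1.5 times as long as one in Arm 1 to register a first event (24/17 = 1.41 on the Table 3 timing). A comparison of proportions reads that extra time as extra risk. Headache, fatigue, insomnia and nausea also occur without interferon, so background events accumulate with calendar time.

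Arm 1 contains the drug that section 8a names as the main source of side effects, and its follow-up is the shortest. If interferon raises the AE rate for four weeks, eight further weeks of background events in the comparators can cancel the excess. The trial could then report similar tolerability when the rates differ, and that result would feed into the larger study this pilot is meant to inform.

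**Working it through.** **Plan's own figure.** The documents give no AE rate and no power for AEs. The only power statement concerns SVR12 (95% v 70%, 50 per arm, above 80%). It reproduces: 92.0% by the normal approximation at two-sided 0.05. This point does not affect it.

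**Inputs.** From the documents: 50 per arm, two-sided 0.05, follow-up of 16 (or 17) and 24 weeks, and 4 weeks on drug in Arm 1. Assumed: a constant background hazard h per week in every arm, with 0.02 as the central value. SOF and DAC are taken to add nothing, in line with section 8a.

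**Method.** P(at least one AE) = 1 − exp(−cumulative hazard). The rejection probability is the exact binomial sum for an uncorrected chi-squared test of Arm 1 against one comparator, without multiplicity correction.

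**1. Equal hazards, h = 0.02**
- Arm 1: 16 × 0.02 = 0.32, giving 27.4%.
- Arm 2 or 3: 24 × 0.02 = 0.48, giving 38.1%.
- The test rejects 20.5% of the time, nearly always with Arm 1 lower.
- With 17 weeks: 0.34, giving 28.8% v 38.1%; rejection 16%.
- With both arms on a common 16-week window, rejection returns to about 5%.

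**2. Raised hazard in Arm 1 while on interferon, h = 0.02**
- Threefold for 4 weeks: 4 × 0.06 + 12 × 0.02 = 0.48, giving 38.1%. This equals the comparator, so the expected difference is zero. With 17 weeks the break-even multiple is (24 − 13)/4 = 2.75.
- Fivefold for 4 weeks: 4 × 0.10 + 12 × 0.02 = 0.64, giving 47.3%.
  - As planned: 47.3% v 38.1%, power about 16%.
  - Common 16-week window: 47.3% v 27.4%, power about 54%.

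**3. Range of background hazards (16 v 24 weeks)**

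| h per week | Equal hazards: rejection | Fivefold: power as planned | Fivefold: power, common 16 weeks |
|---|---|---|---|
| 0.002 | 5.2% | – | – |
| 0.01 | 14% | 11% | 34% |
| 0.02 | 20% | 16% | 54% |
| 0.05 | 34% | 21% | 76% |

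The threefold cancellation holds at every h, because 4 × 3 + 12 = 24.

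**4. Other readings of the window, equal hazards**
- Counting up to 4 weeks of screening in each arm (20 v 28 weeks): 33.0% v 42.9% at h = 0.02. The direction is the same.
- If AEs are in practice captured only to end of treatment (4 v 12 weeks): rejection is 27% at h = 0.01 and 84% at h = 0.05.

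**The case against.** **Equal rates are not what the protocol expects.** The listed events are interferon side effects, and section 8a calls those of SOF and DAC rare. This stands. A reader might infer that Arm 1 will look safer, or that the main danger is a false positive in its favour. The documents do not support that as a general statement: it holds only if the rates are equal. The practical risk is a diluted or hidden Arm 1 excess.

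**The analysis window is inferred.** Section 8c1 is a recording rule, sections 7b and 7c define no window, and the SVR12 visit lists no AE assessment. This stands as a gap in the plan, but it does not remove the imbalance. If capture stops at end of treatment, the ratio is 12/4 = 3 instead of 1.5.

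**Surveillance differs.** Closer contact in Arms 1 and 2 raises detection there, so for Arm 1 v Arm 3 it could offset or even reverse the follow-up effect. This stands. The direction is clearest for Arm 1 v Arm 2, where both have daily field contact during treatment.

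**Serious events.** A reader might extend the point to SAEs. The inflation is absent for rare events (5.2% rejection at 0.002 per week, 1.6% at 0.001). The SAE outcome in 7b also turns on dose modification or discontinuation, which can arise only on treatment. The point is confined to common clinical AEs.

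**Risk per treatment course is a legitimate estimand, and this is a pilot.** Both are true, and a short course is part of the case for Arm 1. But the plan does not name that estimand, and it would still need a stated observation window.

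**Conclusion.** The concern holds for common clinical AEs. As written, the comparison favours Arm 1 through follow-up time alone and can conceal an interferon-related excess. At an assumed 0.02 per week, a threefold on-drug hazard vanishes in expectation, and a fivefold one is detected about 16% of the time instead of 54%. Under equal hazards the nominal 5% test rejects about 20% of the time (16% if Arm 1 is followed for 17 weeks).

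These figures rest on a constant background hazard, no added risk from SOF and DAC, complete AE capture to the end of study, and one uncorrected pairwise test. The documents supply no AE rate, so the size is illustrative. The net direction against Arm 3 is uncertain. SVR12 is untouched. The wording is worth changing before analysis because safety across arms is a stated objective.

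**What to change.** In section 7c:

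- Compare occurrence of clinical AEs over a common window from first dose to Week 16 in all arms.
- Report AE rates per person-week, using a Poisson or negative binomial model with follow-up time as offset, **split into on-treatment and post-treatment periods**. A single overall rate would average Arm 1 over 4/16 = 25% on-drug time and Arms 2 and 3 over 12/24 = 50%. The 16-week window has a similar limit, since it holds 4 on-drug weeks in Arm 1 and 12 in the others.
- List AEs after Week 16 in Arms 2 and 3 descriptively.
- State that AE ascertainment differs by arm. A common window does not cure this: Arms 2 and 3 have no Week 16 visit, and Arm 1 has no scheduled contact between end of treatment and the SVR12 visit.

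Elsewhere, reconcile section 8c1 (AEs recorded through off-drug follow-up) with section 4a5.5 and Table 3 (no AE assessment at SVR12). Also reconcile the Week 16 and Week 17 timings for Arm 1.

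The cost is SAP wording and minor programming, since section 8c1.1 already records AE onset dates. The small downside is that late AEs in Arms 2 and 3 leave the common-window test and appear only in the rates and listings.

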- Obtaining details of concomitant medications and adverse events
- Performing complete physical examination (including retinal examination)
- Obtaining vital signs
- Obtaining body weight and height
- Obtaining blood samples for the tests listed in Table 3
- Obtaining urine sample for β -hCG pregnancy test for females of childbearing potential only
- Chart review of YRG-JHU ICC data to document HIV and antiretroviral therapy status and engagement in opioid substitution therapy (OST)

Subjects who meet all of the inclusion criteria and none of the exclusion criteria will return to the clinic for the Baseline/Day 1 visit assessments and randomization.

4a4. Randomization

A random treatment allocation list will be prepared by a staff member who is not involved in the study using a commercial statistical software package. Blocked randomization will be performed using blocks of randomly

varying sizes of 3, 6 and 9 at a 1:1:1 allocation ratio between the three arms. Blocked randomization will ensure equal distribution of participants between the three arms even if the targeted recruitment numbers are not met. Further, using a variation in the block sizes will minimize the possibility of the study staff being able to identify which arm the next subject would be allocated to. Treatment assignments will be transferred to numbered, opaque, sealed study envelopes by a staff member who is not involved with the study. Envelopes will be opened sequentially by the study physician or research manager as subjects are enrolled. Biometric information (fingerprint data) of the study participant will be recorded prior to randomization assignment.

4a5. Treatment Assessments

4a5.1. Baseline / Day 1 Visit

The following procedures will be completed prior to randomization and dosing/dispensing.

- Perform targeted physical examination
- Obtain vital signs
- Obtain body weight
- Assessment of adverse events and concomitant medications
- Pregnancy prevention counseling for female participants of childbearing potential
- Obtain blood samples for tests listed in Table 3
- Obtain urine sample for β -hCG pregnancy test for females of childbearing potential only
- Collect data from surveys including information on substance use and quality of life
- Adherence counseling
- Chart review of YRG-JHU ICC data to document HIV and antiretroviral therapy status and engagement in opioid substitution therapy (OST)

4a5.2. Treatment administration

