Treatment failure will be defined as HCV RNA > LLOQ (lower limit of quantification) at least 12 weeks after therapy has been completed. Participants who fail treatment will be referred to a government center clinic or their personal physician for follow-up – if participants fail therapy in Arm 1, they will be able to receive 12 weeks of SOF+DAC as is the standard of care.

g. Description of what happens to participants receiving therapy when study ends or if a participant's participation in the study ends prematurely.

Hepatitis C treatment is curative in a large proportion of those who complete a course of therapy. For those who achieve the desired treatment endpoint, sustained virologic response (HCV RNA < LLOQ 12 weeks after treatment is completed), no additional treatment will be needed. Those participants who fail treatment will be considered treatment failures and will be eligible to receive alternate regime.

5. Inclusion/Exclusion Criteria

All participants will be recruited from the Bilaspur ICC. Most of the inclusion/exclusion criteria are related to the use of pegylated interferon. Because we will be randomizing participants, all participants must satisfy the eligibility criteria for pegylated interferon. Our trial is restricted to non-cirrhotics because treatment of cirrhotics with SOF+DAC may require 24 weeks. Other pangenotypic regimens which can be given for 12 weeks such as sofosbuvir and velpatasvir are not yet available in India and so treating cirrhotics is beyond the scope of this study. We will use the FIB-4 to screen for potential cirrhosis. Anyone with a FIB-4 > 3.25 will be referred to the Medical Gastroenterology Department of CIMS for further assessment prior to treatment initiation. In cases where cirrhosis is ruled out after further investigation (e.g., imaging), potential participants can be rescreened for the study.

Inclusion criteria: Subjects must satisfy *all* of the following inclusion criteria listed below to be eligible for participation in this study:

1. Willing and able to provide written informed consent
2. Age \geq 18 years
3. Documented evidence of chronic HCV infection (HCV RNA positive)
4. Participant is a resident of Bilaspur and can provide locator information that can be verified by one of the study staff

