- i. Consistent and correct use of 1 of the following methods of birth control listed below in addition to a male partner who correctly uses a condom from 3 weeks prior to Baseline/Day 1 until the end of treatment. Women of childbearing potential must not rely on hormone-containing contraceptives as a form of birth control during the study. Female subjects using a hormone containing contraceptive prior to screening may continue their contraceptive regimen in addition to the study specified methods of birth control.

- intrauterine device (IUD) with a documented failure rate of less than 1% per year
- female barrier method: cervical cap or diaphragm with spermicidal agent
- tubal sterilization
- vasectomy in male partner

8. Subjects must be of generally good health as determined by the investigator.
9. Subjects must be able to comply with the dosing instructions for study drug administration and be willing to complete the study schedule of assessments.

Exclusion criteria: Subjects who meet *any* of the following exclusion criteria will not be enrolled in the study.

1. Pregnant or nursing female
2. Current or prior history of clinical hepatic decompensation (e.g., ascites, encephalopathy or variceal hemorrhage, MELD<12)
3. Prior treatment for hepatitis C virus infection
4. Infection with hepatitis B virus (HBsAg positive)
5. Chronic use of systematically administered immunosuppressive agents (e.g., prednisone equivalent >10 mg/day)
6. Use of any prohibited concomitant medications within 28 days of the Baseline/Day 1 visit.
7. Contraindications to PEG
8. Known hypersensitivity to the metabolites or formulation excipients of PEG (for Arm 1 subjects)
9. Active significant psychiatric condition(s) including severe depression, severe bipolar disorder and schizophrenia. Other psychiatric disorders are permitted if the condition is well controlled with a stable treatment regimen for ≥ 1 year from screening, or inactive for ≥ 1 year from screening.
10. Presence of autoimmune disorders (e.g., systemic lupus erythematosus, rheumatoid arthritis, sarcoidosis, psoriasis of greater than mild severity)
11. History of clinical significant retinal disease
12. Clinical evidence of cirrhosis

6. Drugs/ Substances/ Devices

a. The rationale for choosing the drug and dose or for choosing the device to be used.

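### Exclusion 2 gives MELD<12 as an example of hepatic decompensation; on the usual scale the sign is reversed, so the example should be corrected or deleted

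*Combined protocol and SAP*

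**What the plan says.** Exclusion criterion 2 (Section 5) removes people with "Current or prior history of clinical hepatic decompensation (e.g., ascites, encephalopathy or variceal hemorrhage, MELD<12"). The lead-in makes the list binding: a subject who meets any one "of the following exclusion criteria will not be enrolled in the study".

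The rest of Section 5 describes the opposite kind of patient. The preamble states "Our trial is restricted to non-cirrhotics because treatment of cirrhotics with SOF+DAC may require 24 weeks" and names the tool for finding cirrhosis: "We will use the FIB-4 to screen for potential cirrhosis". Inclusion 6 sets screening limits on ALT, AST, INR, albumin, direct bilirubin, creatinine clearance, platelets and FIB-4, among others. Inclusion 8 adds "Subjects must be of generally good health as determined by the investigator", and exclusion 12 separately removes anyone with "Clinical evidence of cirrhosis".

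MELD appears only in exclusion 2. The screening procedures in Section 4a3 call for "Obtaining blood samples for the tests listed in Table 3". Neither Table 3 nor the laboratory notes in Section 4a5.6 (for example "Liver function tests (LFT) will include ALT, AST, total and direct bilirubin") asks anyone to compute a MELD score.

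**The concern.** A score below 12 is set beside ascites, encephalopathy and variceal bleeding as a mark of decompensation. If MELD has its usual direction, a low score marks good liver function, so the example describes the intended participants and misses the people it was meant to flag.

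The stake is eligibility. Because any single exclusion bars enrolment, passing inclusion 6 does not rescue someone judged to meet exclusion 2. A literal reader could turn away a suitable person. Someone later checking enrolled participants against the written criteria could find correctly enrolled people apparently ineligible. A site should not have to disregard part of an exclusion criterion in order to enrol the population that the protocol describes.

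**Working it through.** The plan gives no MELD figure to reproduce. The check is of direction only.

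**Assumption.** The documents give neither the formula nor its direction. I use the standard form, with inputs below 1 set to 1:

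MELD = 3.78 × ln(bilirubin) + 11.2 × ln(INR) + 9.57 × ln(creatinine) + 6.43

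Bilirubin is total bilirubin; bilirubin and creatinine are in mg/dl. The laboratory profiles are illustrative and are not taken from the documents.

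**Step 1: which profiles match the printed example?**

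| Bilirubin / INR / creatinine | Calculation | Score | Below 12? |
|---|---|---|---|
| 1 / 1 / 1 | 0 + 0 + 0 + 6.43 | 6.43 | yes |
| 1.2 / 1.2 / 1.2 | 24.55 × ln(1.2) + 6.43 | 10.91 | yes |
| 1 / 1.5 / 1 | 11.2 × ln(1.5) + 6.43 | 10.97 | yes |
| 2 / 1.8 / 1.3 | 2.62 + 6.58 + 2.51 + 6.43 | 18.14 | no |
| 3 / 2 / 1.5 | 4.15 + 7.76 + 3.88 + 6.43 | 22.23 (unrounded terms) | no |

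In the second row, 24.55 = 3.78 + 11.2 + 9.57. If all three inputs rise together, the score reaches 12 at exp((12 − 6.43)/24.55) = exp(5.57/24.55) = 1.25 each. Normal and near-normal profiles match the example; clearly abnormal ones do not.

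**Step 2: does the reversed sign let sick patients in?** The two abnormal profiles have INR 1.8 and 2. Inclusion 6d caps INR at 1.5 × ULN. With an assumed ULN of 1.1 the cap is 1.5 × 1.1 = 1.65, so both fail inclusion 6d unless its allowance for hemophilia or stable anticoagulation applies. The clinical signs in exclusion 2, the FIB-4 limit and exclusion 12 apply regardless.

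**Step 3: what would a corrected sign do?** Some people whom inclusion 6 can admit would then be labelled decompensated:

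- INR 1.65 with the other inputs at 1: 11.2 × ln(1.65) + 6.43 = 12.04. This meets a limit of ≥12; on scores rounded to whole numbers it is 12 and escapes >12.
- Creatinine 2.0 with the other inputs at 1: 9.57 × ln(2) + 6.43 = 13.06. This meets either limit. Inclusion 6g sets a clearance of at least 30 ml/min, not a creatinine value, so it may allow such a person.

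Inclusion 6f limits direct bilirubin while the formula uses total bilirubin, so inclusion 6 does not settle which bilirubin values a corrected limit would catch. The documents contain no distribution of these tests, so no count or share of people affected can be given.

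**The case against.** The strongest reply is that this is a slip any hepatologist would see through. The operative test is clinical decompensation, and MELD is one item in a parenthesis of examples. A person with normal laboratory values and no relevant history has not decompensated, whatever the parenthesis says. Anyone who knows MELD will spot the error, and anyone who does not is never told to calculate it. The working controls are elsewhere, in inclusion 6, the FIB-4 referral and exclusion 12. All of this stands, and it keeps the practical harm small. It does not make the text right: the wrong example still sits in a binding criterion.

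A second reply is that every score above rests on a formula the documents do not give. That is correct. The direction of the scale is the only part of the assumption that the conclusion needs; the decimals are illustrative.

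A third is that the sign could be a fault of text extraction. This is unlikely, since the greater-than signs in exclusions 5 and 9 print correctly.

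A fourth is that reversing the sign, not deleting the example, is the natural repair. The documents do not show whether a MELD limit was intended, so that choice belongs to the sponsor.

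A reader might also infer that the criterion as written would exclude nearly everyone, or that it opens the trial to decompensated patients. The documents support neither. No procedure applies a MELD cut-off, the context points the other way, and the remaining liver criteria are unaffected.

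**Conclusion.** The point holds as a wording error in an operative eligibility criterion, with limited consequences. Assuming the standard MELD direction, the printed sign is reversed: a normal profile scores 6.43 and matches the exclusion example, while profiles scoring 18.14 and 22.23 do not. This contradicts the population that Section 5 describes.

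The harm depends on someone reading the example literally, and its frequency cannot be estimated from the documents. Liver-safety screening, sample size, power and the analysis are unaffected. It is worth correcting because the text is binding and the repair is nearly free.

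**What to change.** Correct or delete the example. Deletion is simplest: end the parenthesis in exclusion 2 after variceal hemorrhage. It costs one phrase, needs no new test, visit, form or calculation, and leaves the other liver criteria in place.

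If the sponsor did intend a MELD limit, change the example to MELD >12 or ≥12, state the formula and the rounding rule, and add the calculation to screening. No new blood test is needed, because Table 3 already has prothrombin time, liver function and renal function at screening. The cost is that some people who meet inclusion 6, for example with raised INR or raised creatinine, would be excluded. The sponsor should also say how such a limit fits with inclusion 6d, which tolerates a raised INR in known hemophilia or stable anticoagulation.
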